During the entire study period, adverse events will be closely monitored by the trial PI and clinical trial coordinator of this study, working along with the study DSMB. In particular, formal stopping rules on the 6-month mortality are stipulated in this protocol (please refer to section 4.1 “Efforts to minimize procedure risks”). In addition, in the event that other adverse events (e.g., surgical complications) are thought to be excessive for the study patient population at any point of the trial, the patient accrual to the trial will be suspended immediately, pending a review of all adverse events data. A final decision will be made by the trial PI and DSMB as to whether the trial should be amended, terminated or continue accrual. Such decision should be filed with and pre-approved by the institutional IRB.

2.4 Study Endpoints:

The primary safety endpoint is procedural success at 30-days. Procedural success will include:

- Successful vascular access without unplanned major vascular complication as defined by VARC-2, delivery and retrieval of the transcatheter valve delivery system, correct position of both the vascular stent(s) and transcatheter valve in the IVC, a single valve placed within the IVC, and no need for additional surgery or re-intervention (including drainage of pericardial effusion) with the patient being alive at 30-days.

The primary efficacy endpoint will be improvement in one of three variables assessed from baseline to 6-months.

- Improvement of KCCQ score >15. This has been shown to correlate with improvement in quality of life with heart failure patients²².
- Improvement in 6-minute walk test (6MWT)>70 meters. This has been shown to provide prognostic information in patients with congestive heart failure after an intervention²³.
- Improvement of greater than 6% of peak Vo2 in cardiopulmonary exercise testing. In a heart failure population, this has been shown to help assess prognosis in patients who were instituted in an exercise program ²⁴.

Secondary endpoints will be evaluated at several timepoints and will be divided into safety and efficacy: The first in the acute setting which will be out to 30 days or hospital discharge whichever being longer; additional time points will be at midterm (6 months post-procedure), long term (1 year and annually up to 5-years post-procedurally.)

Secondary safety endpoints include:

- All stroke and TIA (VARC-2)
- Mortality (VARC-2)
- Myocardial infarction (VARC-2)

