5.2.1 Placement of percutaneous aortic valve in the inferior vena cava

The procedure will be performed in the cath lab/ hybrid Cath Lab/OR under general anesthesia and transesophageal echocardiographic as well as fluoroscopic guidance.

Measurements obtained prior to the procedure

The diameter of the IVC at the RA/IVC junction will be measured prior to the procedure by contrast CT or rotational cine fluoroscopy to determine sizing of the stent which will be placed in the IVC. In order to avoid compromise of the hepatic veins with the valve skirt, distances from the RA/IVC junction to the hepatic veins will be measured by contrast CT.

Procedure

The procedure will be performed through the right or left femoral vein using standard technique. We will use fluoroscopic and ultrasonographic landmarks to locate the right femoral vein and using a micropuncture needle for initial access, and then will place an 8F sheath in the right Common Femoral vein. We will then perform a cavogram using a Omnipulse catheter. The Edwards expandable sheath and delivery system will be placed into the right femoral vein. A 5-French sheath will be placed in the right or left radial femoral artery to monitor arterial pressure and secure arterial access throughout the procedure, and a catheter may or may not be placed in the right internal jugular vein. Heparin will be administered to achieve an activated clotting time (ACT) between 250-300s. To achieve stable position of the valve in the IVC, we will perform pre-stenting of the IVC with either a balloon expandable or self-expandable stent according to standard technique. A repeat cavogram with an Omnipulse catheter will be done to delineate the takeoff of the hepatic veins prior to valve implantation. When positioning is confirmed the Edwards or balloon in balloon (BIB) delivery system will be deployed into the suprahepatic segment of the IVC by standard technique. Right ventricular (RV) angiography from IJ access and echocardiogram will be performed to confirm intact valve function and any evidence of regurgitation. At the end of the procedure, the venous sheath will be removed and periclose devices will be deployed or a figure of 8 suture will be used to achieve adequate hemostasis. The arterial sheath will be removed with closure devices or with direct manual pressure.

Anticoagulation Regimen:

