5.5 Follow-Up Procedures

Patients will follow up at 1, 6 and 12 months with a member of the study team. The following information will be collected at follow up visits.

Systems:

- Physical Exam. This will include vital signs and weight, head, ears, eyes, nose and throat (HEENT), neck, lungs, cardiovascular, abdomen, genitourinary, gastrointestinal, musculoskeletal, neurological
- NYHA functional Class as per The Criteria Committee of the New York Heart Association. *Nomenclature and Criteria for Diagnosis of Diseases of the Heart and Great Vessels*. 9th ed. Boston, Mass: Little, Brown & Co; 1994:253-256
- Diuretic types and doses
- Event assessment as per VARC-2 ¹⁹.

Laboratory Measurements

- CBC with differential
- Comprehensive metabolic panel
- Brain Natriuretic Peptide (BNP)
- Haptoglobin
- Lactate Dehydrogenase (LDH)

Non-Invasive Tests

- ECG
- Chest X-ray (portable or PA and lateral)
- Echocardiogram (Transthoracic)
- Chest and Abdominal CT (6-months only)
- Cardiopulmonary Exercise Stress test ³² (6-months only)

Functional Assessments

- 6-minute walk test ³³
- Villalta Scale ^{25,26}
- EORTC QLQ-C30 ²⁷
- ESAS-AM ²⁸
- Kansas City Cardiomyopathy Questionnaire (KCCQ) ²²

Invasive studies

- Right heart catheterization (6-months only)

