Overt bleeding either associated with a drop in the hemoglobin level of at least 3.0 g/dL or requiring transfusion of 2 or 3 units of whole blood/RBC, or causing hospitalization or permanent injury, or requiring surgery AND
Does not meet criteria of life-threatening or disabling bleeding
Minor bleeding (BARC type 2 or 3a, depending on the severity)
Any bleeding worthy of clinical mention (eg, access site hematoma) that does not qualify as life-threatening, disabling, or major

BARC, Bleeding Academic Research Consortium²⁹; *RBC*, red blood cell. *Given that 1 unit of packed RBC typically will raise the hemoglobin concentration by 1 g/dL, an estimated decrease in hemoglobin will be calculated.

TABLE 6. Acute kidney injury (AKIN classification*)

Stage 1
Increase in serum creatinine to 150%-199% (1.5-1.99 \times increase compared with baseline) OR increase of ≥ 0.3 mg/dL (≥ 26.4 mmol/L) OR
Urine output <0.5 mL/kg/h for >6 but <12 h
Stage 2
Increase in serum creatinine to 200%-299% (2.0%-2.99% increase compared with baseline) OR
Urine output <0.5 mL/kg/h for >12 but <24 h
Stage 3†
Increase in serum creatinine to $\geq 300\%$ (>3 \times increase compared with baseline) OR serum creatinine of ≥ 4.0 mg/dL (≥ 354 mmol/L) with an acute increase of at least 0.5 mg/dL (44 mmol/L) OR
Urine output <0.3 mL/kg/h for ≥ 24 h OR
Anuria for ≥ 12 h

The increase in creatinine must occur within 48 h. *Mehta et al.³¹ †Patients receiving renal replacement therapy are considered to meet Stage 3 criteria irrespective of other criteria.

TABLE 7. Vascular access site and access-related complications

Major vascular complications
Any aortic dissection, aortic rupture, annulus rupture, left ventricle perforation, or new apical aneurysm/pseudoaneurysm OR
Access site or access-related vascular injury (dissection, stenosis, perforation, rupture, arterio-venous fistula, pseudoaneurysm, hematoma, irreversible nerve injury, compartment syndrome, percutaneous closure device failure) leading to death, life-threatening or major bleeding,* visceral ischemia, or neurological impairment OR
Distal embolization (noncerebral) from a vascular source requiring surgery or resulting in amputation or irreversible end-organ damage OR
The use of unplanned endovascular or surgical intervention associated with death, major bleeding, visceral ischemia or neurological impairment OR

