Valve malpositioning	
Valve migration
 
After initial correct positioning, the valve prosthesis moves upwards or downwards, within the aortic annulus from its initial position, with or without consequences

Valve embolization	The valve prosthesis moves during or after deployment such that it loses contact with the aortic annulus
Ectopic valve deployment	Permanent deployment of the valve prosthesis in a location other than the aortic root
TAV-in-TAV deployment	An additional valve prosthesis is implanted within a previously implanted prosthesis because of suboptimal device position and/or function, during or after the index procedure

TAVI, Transcatheter aortic valve implantation; THV, transcatheter heart valve.
*Durack et al.⁷²

TABLE 10. Prosthetic valve dysfunction

Prosthetic aortic valve stenosis*			
	Normal	Mild stenosis	Moderate/severe stenosis
Quantitative parameters (flow-dependent)†			
Peak velocity (m/s)	<3 m/s	3-4 m/s	>4 m/s
Mean gradient (mm Hg)	<20 mm Hg	20-40 mm Hg	>40 mm Hg
Quantitative parameters (flow-independent)			
Doppler velocity index‡	>0.35	0.35-0.25	<0.25
Effective orifice area§	>1.1 cm ²	1.1-0.8 cm ²	<0.8 cm ²
Effective orifice area	>0.9 cm ²	0.9-0.6 cm ²	<0.6 cm ²
Prosthesis-patient mismatch (PPM)			
	Insignificant	Moderate	Severe
Indexed effective orifice area¶ (cm ² /m ²)	>0.85 cm ² /m ²	0.85-0.65 cm ² /m ²	<0.65 cm ² /m ²
Indexed effective orifice area# (cm ² /m ²)	>0.70 cm ² /m ²	0.90-0.60 cm ² /m ²	<0.60 cm ² /m ²
Prosthetic aortic valve regurgitation			
	Mild	Moderate	Severe
Semiquantitative parameters			
Diastolic flow reversal in the descending aorta—PW	Absent or brief early diastolic	Intermediate	Prominent, holodiastolic
Circumferential extent of prosthetic valve paravalvular regurgitation (%)**	<10%	10%-29%	≥30%
Quantitative parameters‡			
Regurgitant volume (mL/beat)	<30 mL	30-59 mL	≥60 mL
Regurgitant fraction (%)	<30%	30-49%	≥50%
EROA (cm ²)	0.10 cm ²	0.10-0.29 cm ²	≥0.30 cm ²

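### The VARC-2 major vascular complication used in the safety endpoints names implant-site injury only for the aorta, annulus and left ventricle, so some IVC implant injuries can be scored as procedural success

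*Combined protocol and SAP*

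**What the plan says.** Section 2.4 builds the primary safety endpoint, procedural success at 30 days, from several components. One is "Successful vascular access without unplanned major vascular complication as defined by VARC-2". The others are delivery and retrieval of the system, "correct position of both the vascular stent(s) and transcatheter valve in the IVC", a single valve, no further surgery or re-intervention (drainage of a pericardial effusion counts as one), and survival to 30 days. Major vascular complication by VARC-2 also stands alone in the list of secondary safety endpoints.

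The definition is in Appendix B, Table 7. Its first clause reads "Any aortic dissection, aortic rupture, annulus rupture, left ventricle perforation, or new apical aneurysm/pseudoaneurysm OR" and carries no severity condition. The next clause covers injury at or related to the access site, but only when it leads to death, life-threatening or major bleeding, visceral ischemia or neurological impairment. Later clauses cover distal embolization with serious consequences, unplanned intervention associated with a similar list of outcomes, leg ischemia and nerve injury.

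Section 5.2.1 sets the target site: the "delivery system will be deployed into the suprahepatic segment of the IVC by standard technique". The protocol foresees harm there. Section 4.0 lists stent migration and damage to vessels or the heart from IVC stenting, and section 5.2.1 measures the distance to the hepatic veins so that the valve skirt does not compromise them.

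Sections 5.3 to 5.6 also call for "Event assessment as per VARC-2". In Table 9, ectopic deployment is "Permanent deployment of the valve prosthesis in a location other than the aortic root", migration means that "the valve prosthesis moves upwards or downwards, within the aortic annulus from its initial position, with or without consequences", and embolization is "The valve prosthesis moves during or after deployment such that it loses contact with the aortic annulus". Table 10 grades stenosis and regurgitation of an aortic prosthesis.

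**The concern.** In an aortic implant, the first clause of Table 7 captures damage done by the device where it is placed, whatever its consequences. Here the device is placed elsewhere, and the clause was not moved with it. The corresponding injuries are perforation, rupture or dissection of the IVC, hepatic veins or right atrium. They are not named, and they count only if they fit a clause written for something else. The pivotal judgement is whether an injury caused by the stent or valve is access-related, and the text gives no rule for making it.

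This is a safety and feasibility study at four sites. The core-laboratory review in section 2.2.2 covers baseline imaging. The protocol text describes no event adjudication for this trial; section 4.1.2 mentions an adjudication committee only when restricting who may sit on the DSMB. What is at stake is whether the main safety proportion, and the secondary vascular complication rate, count the injury most specific to this implant.

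The Table 9 wording is a lesser matter of event reporting. Migration and embolization are real risks (section 4.0 names both, and section 1.0 describes a caval valve that embolized into the right atrium in sheep), yet their definitions refer to a structure that this valve never touches.

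**Working it through.** The plan states no figure that depends on this definition, so there is none to reproduce. The check has two parts.

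**1. Applying the definitions to cases.** Take a stent- or valve-related tear of the IVC, with all other components of procedural success met. MVC is the major vascular complication of Table 7.

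| Case | Primary endpoint | Secondary endpoint (MVC) |
|---|---|---|
| A. Needs additional surgery, no listed consequence, alive at 30 days | Fails (surgery component) | Not met unless the intervention comes with a listed outcome |
| B. Death by 30 days, no intervention | Fails (death component) | Met only if judged access-related; the death counts under mortality |
| C. Major bleeding, managed conservatively, alive, judged access-related | Fails (MVC) | Met |
| D. As C, but judged not access-related | **Success** | **Not met** |
| E. No listed consequence, observed only, alive | **Success** | **Not met** |
| For comparison: aortic dissection with the course of E | Fails (MVC, first clause) | Met |

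C and D are the same clinical event and differ only in the access-related judgement. E and the comparison row have the same course and differ only in the vessel. A and B show that the secondary endpoint lacks the protection that the surgery and death components give the primary. Hepatic vein occlusion with visceral ischemia, not judged access-related and not re-intervened on, is scored as in D.

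**2. Scale.** Inputs from section 2.3: up to 15 patients, and a point estimate with an exact binomial interval. The 95% Clopper-Pearson limits for x successes in n are

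- lower = Beta quantile at 0.025 with parameters x and n − x + 1;
- upper = Beta quantile at 0.975 with parameters x + 1 and n − x.

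For x = n the upper limit is 1 and the lower reduces to 0.025^(1/n).

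- 15/15 = 100%: lower 0.025^(1/15) = 0.782, so 78.2% to 100%.
- 14/15 = 93.3%: 68.1% to 99.8%.
- 13/15 = 86.7%: 59.5% to 98.3%.

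Each reclassified patient moves the estimate by 1/15 = 6.7 percentage points. The documents give no rate for these injuries, so zero to two patients is an assumed range.

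**The case against.** The strongest reply is that the gap is narrow. Surgery, re-intervention, pericardial drainage and death by 30 days already fail the primary endpoint, and several Table 7 clauses are not tied to the aorta. Serious injuries are reported to the DSMB chair within 24 hours and reviewed by the DSMB (section 7.2), so they are not lost to oversight. There is no performance goal or power calculation, so one reclassified patient crosses no threshold, and the intervals above overlap heavily. Data go through one system and one coordinating center, so divergence between sites is possible but not shown. All of this stands. It limits the size of the problem but leaves cases D and E scored as successes.

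A reader might infer something stronger: because every correct implant is literally ectopic, the primary safety endpoint would count every success as a complication. The documents do not support that. Section 2.4 sets its own position criterion, in the IVC. Ectopic deployment, migration, embolization as defined in Table 9 and the Table 10 gradients enter no endpoint, stopping rule or pause rule, and section 2.3 tabulates adverse events by CTCAE version 4.0.

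Nor is all of Appendix B unusable. The definitions of mortality, myocardial infarction, stroke, bleeding and kidney injury do not depend on the implant site. Neither does valve thrombosis, which drives the pause rule in section 4.1.3.

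**Conclusion.** The point holds for the major vascular complication definition. As written, an injury of the IVC, hepatic veins or right atrium from the stent or valve can be scored as procedural success when it is not judged access-related, gets no surgery or re-intervention and is survived to 30 days. The standalone secondary endpoint is more exposed. This is a stated rule that misclassifies, not merely a missing detail, and it should be settled before events have to be classified.

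The size is illustrative: 6.7 percentage points per reclassified patient if all 15 are enrolled, with no injury rate available. The ectopic, migration and embolization wording is a defect of event assessment only.

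The conclusion assumes that no adaptation exists in the CRF addendum (section 8.1) or in pages not available for this review. Sections 2.4 and 5.3 to 5.6 and Appendix B point to none.

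**What to change.** Add one IVC-adapted definition table to Appendix B, cite it in section 2.4 and match the CRF wording.

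1. Count stent- or valve-related perforation, rupture or dissection of the IVC, hepatic veins or right atrium as a major vascular complication, in parallel with Table 7's unqualified first clause. Attaching the severity conditions of the access clause instead would leave case E scored as success. State whether occlusion of the IVC or a hepatic vein counts on its own or only with the listed consequences.
2. Define correct position, migration and embolization relative to the IVC landing zone, the RA/IVC junction and the hepatic vein os. Appendix A already has the post-implant echocardiogram record valve position against the last two. For the 30-day endpoint use the 24-hour and 30-day echocardiograms in Table 1 of the protocol; the follow-up CT comes only at 6 months.
3. Mark ectopic deployment and the Table 10 aortic gradients as not applicable.

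The cost is one table and matching form wording; the assessments are already scheduled. The safety endpoint becomes slightly stricter and less directly comparable with aortic series.

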APPENDIX C: HOVER CT PROTOCOL AND PATIENT DOSE ESTIMATION

Scanner: Philips iCT 256

Dose estimation for an average adult (BMI < 30 and equivalent to 32 cm. diameter water equivalent phantom)

I. CT Protocol:

Scan 1: Topogram

Dual projection – Cardiac chest and upper abdomen
Centered around the diaphragm

Scan 2: Spiral Retrospectively ECG Gated acquisition

Single Post-contrast phase
FOV: Z –Axis: Superior cardiac margin down to T12 vertebra (~10-12 cm)

kVp	- 100 kVp for BMI < 30; 120 kVp for BMI > 30
mAs (mA)	- 400(242) @ 100 kVp
Beam collimation	- 0.6 x 128 mm
Pitch	- 0.2
Gantry speed	- 0.27 s

Contrast: Omnipaque 350 IV, 60 cc @ 5 cc/s followed by saline 30 cc @ 5 cc/s.
Bolus track in MPA; 150 HU threshold; Minimum scan delay

Reconstruction:

Iterative reconstruction (iDose (L3) / IMR (L1) as required)

Phases: 20%, 30%, 40% R-R interval

Multiphase: 0 – 90%

Axial slice thickness/overlap – 0.8 mm/50%

COR & SAG Reconstruction 1 mm.

Axial slice thickness 3 mm (ST Kernel)

II. Patient Dose estimation:

Scan	mAs^2	kV^2	CTDI vol mGy	DLP $\text{mGy}^* \text{cm.}$	Z axis FOV cm.
Topogram	30	120	0.01	1.5	30 cm.
Spiral	400	100	15.4	265	12 cm ¹ .

Total DLP (1.5 + 265) = 266.5 mGy-cm.

Estimated Effective Dose = 271.5 mGy-cm. x 0.015 = ~ 3.8 mSv (3.5 - 4.5 mSv)

1. Z axis FOV for spiral scanning will be superior cardiac margin down to T12 vertebra.
2. Exposure factors will be adjusted depending on the patient's BMI (i.e. smaller than normal BMI < 20 and larger than normal BMI > 30). Automatic Exposure Control (Cardiac DoseRight) will be utilized as appropriate.
3. Effective dose conversion factor based on European guidelines on quality criteria for computed tomography EUR 16262.

All studies are supervised by a Board certified Radiologist.

APPENDIX D: INCLUSION/EXCLUSION CHECKLIST

I. Study Information

Protocol Title:	Heterotopic Implantation Of the Edwards-Sapien 3 Transcatheter Aortic Valve in the Inferior Vena cava for the treatment of severe tricuspid Regurgitation
IRB Number:	
Principal Investigator:	[name]

II. Inclusion/Exclusion Criteria

Inclusion Criteria (From IRB-approved protocol)	Yes	No	Supporting Documentation*
1. Patients must be at least 21 years old			
2. The patient must have severe, symptomatic (ACC/AHA Stage D symptoms) tricuspid regurgitation (TR) as assessed by 2D echocardiogram with evidence of peripheral and central venous congestion (specifically lower extremity edema and abdominal ascites requiring diuretics.)			
3. The patient must be evaluated by a "heart team" of physicians including an interventional cardiologist, cardiothoracic surgeon, heart failure specialist, and imaging specialist, and presented for review at a local multidisciplinary conference. By consensus, the heart team must agree (and verify in the case review process) that valve implantation will likely benefit the patient.			

4. The heart team must agree that medical factors preclude operation, based on a conclusion that the probability of death or serious, irreversible morbidity exceeds the probability of meaningful improvement. Also, other factors which may increase the patients perceived surgical risk for inclusion in the trial will be clearly delineated if they are present. These include, but are not limited to the following as defined by VARC 2: Frailty, Hostile chest, porcelain aorta, IMA or other critical conduit crossing the midline or adherent to the posterior table of sternum, severe right ventricular (RV) dysfunction. The surgeons' consultation notes shall specify the medical or anatomic factors leading to that conclusion. At least one of the cardiac surgeon assessors must have interviewed and examined the patient.
			

5. The study patient provides informed consent and agrees to comply with all required post-procedure follow-up visits, including annual visits up to 5 years
			
Exclusion Criteria (From IRB-approved protocol)			

1. Heart Team assessment of operability (the heart team considers the patient to be a good surgical candidate)
			

2. Evidence of an acute myocardial infarction \leq 1 month (30 days) before the intended treatment [defined as: Q wave MI, or non-Q wave MI with total CK elevation of CK-MB \geq twice normal in the presence of MB elevation and/or troponin level elevation (WHO definition)]
			

3. Untreated, severe, left sided valvular heart disease including mitral regurgitation or stenosis, and aortic regurgitation or stenosis
			

4. Mean pulmonary artery pressures ≥ 40 mmHG and PVR > 4 Woods units as assessed by right heart catheterization			
5. Any therapeutic invasive cardiac procedure resulting in a permanent implant that is performed within 30 days of the index procedure. Examples of permanent implant would include any new heart valve. Implantation of a permanent pacemaker is excluded.			
6. Patients with planned concomitant surgical or transcatheter ablation for Atrial Fibrillation			
7. Leukopenia (WBC < 3000 cell/mL), acute anemia (Hgb < 9 g/dL), Thrombocytopenia (Plt $< 50,000$ cell/mL)			
8. Hemodynamic or respiratory instability requiring inotropic support, mechanical ventilation or mechanical heart assistance within 30 days of screening evaluation			
9. Need for emergency surgery for any reason			
10. Left ventricular ejection fraction $< 40\%$			
11. Echocardiographic evidence of intra-cardiac mass, thrombus or vegetation			
12. Active upper GI bleeding within 3 months (90 days) prior to procedure			
13. A known contraindication or hypersensitivity to all anticoagulation regimens, or inability to be anticoagulated for the study procedure			
14. Recent CVA clinically confirmed (by neurologist) or neuroimaging confirmed stroke or transient ischemic attack (TIA) within 6 months (180 days) of the procedure			
15. Estimated life expectancy < 1 year			

16. Expectation that patient will not improve despite treatment of tricuspid regurgitation			
17. Currently participating in another investigational cardiac device study or any other clinical trial, including drugs or biologics. Note: Trials requiring extended follow-up for products that were investigational, but have since become commercially available, are not considered investigational trials			
18. Active bacterial endocarditis within 6 months (180 days) of procedure			
19. Patients with signs or symptoms of SVC syndrome, or hepatic cirrhosis not felt due to passive congestion from TR			
20. Subject unable to personally provide informed consent			
21. FEV1<30% of predicted			
22. MELD score >21			

*All subject files must include supporting documentation to confirm subject eligibility. The method of confirmation can include, but is not limited to, laboratory test results, radiology test results, and medical record review.

III. Statement of Eligibility

This subject is **eligible** / **ineligible** for participation in the study.

Signature:	Date:
Printed Name:	

